A Data Safety Monitoring Board (DSMB), consisting of three individuals appointed by a third-party contractor, will meet as scheduled by this protocol to review safety throughout study conduct. Specifically, the DSMB will meet to assess the progress of the first five patients with mild symptoms after their second infusion, and a decision on continuation of study will be made prior to the third infusion (day 7). The same will occur for the first five patients experiencing severe symptoms after their second infusion, and a decision on continuation of study will be made prior to their third infusion (day 14). All other patients may be screened beforehand so that enrollment may occur once the committee declares it may resume. DSMB is scheduled for at least 3 meetings pertaining to this protocol: after the mild symptom group receives their second infusion, after the severe symptom group receives their second infusion, and at study midpoint. Additional meetings may be necessary, upon request from the Medical Monitor.

DSMB will review all deaths (to assure non-attribution), cases of anaphylaxis or suspected anaphylaxis, thromboembolic events, new malignancy/tumor, infections/hospitalizations (including unrelated to COVID-19 but due to underlying condition). DSMB will also review safety data at mid-point of the study.

Risks

Potential Risks of the Investigational Product and Clinical Investigation

Risks Associated with HB-adMSCs

Respiratory Risks:

A potential risk is that the infusion could initiate a VTE event with subsequent

cardiopulmonary sequelae of respiratory failure and/or right heart strain/failure. We plan to monitor oxygen saturation, and respiratory rate/work of breathing for the first 2 hours post-infusion. The patient will be examined for VTE events (clinical exam, oxygen saturation) during each infusion visit and at each follow-up visit.

Hepatic Risks:

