Safety is assessed by primary and secondary endpoints. Primary safety endpoints include incidence of adverse and serious adverse events. Secondary safety endpoints include incidence of specific adverse events including serious infections, infusion-related reactions, hepatotoxicity, heart failure, and cytopenias. Clinically significant changes in laboratory values, vital signs, weight, and physical examination results will also be measured.

Clinical efficacy is assessed by primary and secondary endpoints. Primary endpoints include the change from baseline in inflammatory markers (IL-6, D-dimer, C Reactive protein), time to clearing PCR test, change from baseline oxygenation, and time to return to room air (RTRA). Secondary endpoints include change from baseline of chest x-ray, change from baseline of CT scan, change from baseline of clinical laboratory values, adverse and serious adverse events, change in exploratory markers, and change in ordinal scale.

Analysis Population

Safety: All subjects receiving at least one infusion will be included for safety analysis.

Efficacy: All subjects receiving all four infusions will be included for efficacy analysis.

Additional sub-analysis will be performed comparing subjects receiving any other experimental treatment for COVID-19, to those who are not, in the following items:

- Change from baseline oxygenation
- Change from baseline chest x-ray
- Change from baseline CT scan
- Time to clearing PCR test
- Change from baseline inflammatory markers (IL-6, D-dimer, C Reactive protein)
- Change from baseline in IL-10
- Change from baseline in CD4:CD8 ratio
- Change from baseline in CD3⁺CD56⁺
- Change from baseline in VEGF
- Change from baseline in the 7-point ordinal scale

Demographic and Baseline Characteristics

Information describing subjects' gender, race/ethnicity, and age will be displayed in tables similar to the ones included below. The number and percent of the total sample population will be calculated for each demographic category.

Demographics	Female		Male		Both Genders	
Race/Ethnicity	N	%	N	%	Total	%
White						
Black or African American						
Hispanic or Latino						
Other (Specify)						
Total						

The mean, minimum, and maximum age at enrollment will be determined using standard calculations. The number and percent of total subjects in each age group will be calculated and reported.

Age at Enrollment	N	%
Mean		
Minimum		
Maximum		
	N	%
≥ 18 years		
18-21 years		
22-29 years		
30-39 years		

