## 2. SUMMARY OF KEY PROTOCOL INFORMATION

### 2.1. Study Objective(s) and Endpoint(s)

Objectives	Endpoints
Primary Objective	Primary Endpoint

To investigate the safety and efficacy of HB-adMSCs in the treatment of patients with COVID-19 by decreasing inflammation, improving oxygenation, and decreasing time to return to room air (RTRA)

	

Change from baseline in inflammatory markers (TNF-alpha, IL-10, IL-6, C-Reactive protein)

Change from baseline oxygenation

Time to return to room air (RTRA) and proportion of patients with room air status

Secondary Objectives	Secondary Endpoints

Objectives	Endpoints

• To investigate the safety and efficacy of HB-adMSCs in improving clinical status of patients suspected to have COVID-19).

	

• Change in clinical laboratories

• Change from baseline Chest X-ray

• Change from baseline CT scan

• Change from baseline in exploratory markers (D-dimer, myoglobin, troponin, creatinine kinase, serum ferritin, CD3CD56, CD4/CD8, VEGF)

• Time to negative PCR test results

• Change from baseline in the 7-point ordinal scale

• Cumulative incidence of serious adverse events (SAEs) or adverse events (AEs)

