#### **7.2.4.2. Data Analytic Models**

All secondary endpoint efficacy measurements available at post-baseline at scheduled measurements (Visits 2 through 5 [infusions 1 through 4] for exploratory markers and clinical labs; Visits 2 through 6 [infusion 1 through end of treatment] for chest X ray, CT scan, and ordinal scale score) will be analysed in a generalized linear mixed model. The model will predict each outcome as a function of the interaction between the fixed factors treatment group and time, controlling for lower order effects of time and treatment group. Models will control for stratification variables (see [Covariates and Other Strata](#)), and subject will be included as random effects. AEs/SAEs and AE severity will be analyzed as dichotomous outcomes (whether patient exhibited AE/SAE at any time during the study). AE/SAE attribution to study drug will be analyzed as count outcomes. All models will control for stratification variables.

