#### **8.1. Adverse Events Analyses**

AEs will be coded using the most recent version of the Medical Dictionary for Regulatory Activities (MedDRA).

A treatment emergent adverse event (TEAE) is defined as an event that has onset date on or after the first day of exposure to infusion treatment and no later than 3 days after the last day of infusion treatment. Here the first day of exposure is defined as the first day of exposure to infusion treatment.

Treatment Adverse events (TAES) are summarised descriptively, whereas non-TEAEs are presented in listings. TAE data will be displayed in terms of the number of subjects with at least one event (N), percentage of subjects with at least one event (%) and the number of events (E).

Summaries of TAEs and of serious AEs will be presented as an overview including all AEs, serious AEs, AEs by severity, AEs by relation to treatment, action to AEs and treatment advised, and outcome of AEs.

Furthermore, summary tables based on system organ class and preferred terms are made for:

- All TAEs
- Serious AEs
- AEs leading to withdrawal of study

Individual adverse events will be listed.

The details of the planned displays are in **Error! Reference source not found..**

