## **8.2. Clinical Laboratory Analyses**

Laboratory evaluations including the analyses of Biochemistry laboratory tests (includes Comprehensive Metabolic Profile), Hematology laboratory tests (Complete Blood Count (CBC) and Coagulation Panel) and Urinalysis. The details of the planned displays are in **Error! Reference source not found..**

All laboratory parameters, including numerical urine analysis parameters will be summarised descriptively. Categorical urine analysis results will be summarized using count and percentage based on subjects.

Results of urine pregnancy test will be listed in individual subject data listings only.

Individual laboratory evaluations will be listed. In addition, a listing containing individual subject laboratory values outside the normal reference ranges will be provided.

Data recorded at unscheduled assessments will not be included in tables and figures but will be listed.

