## **8.3. Other Safety Analyses**

The analyses of non-laboratory safety test results including physical examination and vital signs. The details of the planned displays are presented in **Error! Reference source not found..**

Physical Examination and Vital signs will be summarized using count and percentage based on subjects. The vital signs based on visit and change from baseline will be summarized using descriptive statistics.

Individual Vital signs, Physical Examination evaluations will be listed.

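### The SAP text gives no definition, term grouping or by-arm incidence for the protocol's five named secondary safety endpoints or for thromboembolic events, and no dedicated count of deaths by arm to Day 28

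*SAP*

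**What the plan says.** Two places in the protocol, Criteria for Evaluation in the Synopsis and Endpoints under Statistical Analysis, state: "Secondary safety endpoints include incidence of specific adverse events including serious infections, infusion-related reactions, hepatotoxicity, heart failure, and cytopenias". Under Respiratory Risks the protocol adds: "A potential risk is that the infusion could initiate a VTE event with subsequent" cardiopulmonary consequences. The DSMB section puts deaths and thromboembolic events on the board's review list.

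The protocol's other lists are thinner. The Study Endpoints lists in the Synopsis and the body, and the Safety Analysis paragraph, do not mention the five categories. They refer only to AEs and SAEs as a whole.

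The SAP follows the thinner lists. Its only adverse-event endpoint (SAP 2.1, repeated in 7.2.1) is "Cumulative incidence of serious adverse events (SAEs) or adverse events (AEs"). Its adverse-event content is then:

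- SAP 7.2.4.2, models: "AEs/SAEs and AE severity will be analyzed as dichotomous outcomes (whether patient exhibited AE/SAE at any time during the study"), plus attribution as a count.
- SAP 8.1, overview: all AEs, serious AEs and severity, with "AEs by relation to treatment, action to AEs and treatment advised, and outcome of AEs".
- SAP 8.1, detail: "Furthermore, summary tables based on system organ class and preferred terms are made for" all treatment AEs, serious AEs and AEs leading to withdrawal.
- SAP 8.2, laboratory: "All laboratory parameters, including numerical urine analysis parameters will be summarised descriptively", with a listing of out-of-range values.

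**The concern.** An endpoint that the protocol names should have a definition, an analysis set and a planned result. Here the SAP can be followed to the letter and the report will still hold no incidence, by arm, for any of the five. Someone would then have to assemble them from coded terms, probably with the allocation known, and the choice of terms could move the answer.

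There is also a question of sensitivity. An infusion reaction or a thromboembolic event can be coded under several preferred terms and more than one organ class. With 60 and 40 patients, a modest excess spread over several rows leaves little to see in each. The grouped count is the one that could show it.

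**Working it through.** **Coverage.** Each item is set against the SAP text.

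| Item | Basis in protocol | What the SAP text offers | By-arm incidence specified? |
|---|---|---|---|
| Serious infections | Secondary safety endpoint | Possibly much of it in one organ-class row of the SAE table | No |
| Infusion-related reactions | Secondary safety endpoint | Organ-class and term rows only | No |
| Hepatotoxicity | Secondary safety endpoint; AST/ALT criterion under Hepatic Risks | Metabolic panel summarised and modelled (7.2, 8.2); the criterion is not used | No |
| Heart failure | Secondary safety endpoint | Organ-class and term rows only | No |
| Cytopenias | Secondary safety endpoint | Blood counts summarised and modelled; no threshold | No |
| Thromboembolic events | Named risk; DSMB review item | Organ-class and term rows; coagulation values | No |
| Death | DSMB review item; fatal events are SAEs | SAE tables, AE outcome, category 1 of the ordinal scale | No dedicated count |

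The tally for the five named endpoints is 0 of 5 defined, grouped or compared. Two of the five have indirect laboratory data.

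**Why the routes for death do not add up to a count.**

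- The ordinal model uses the efficacy analysis set (SAP 7.2.3), which requires all four infusions (SAP 4). A patient who dies before infusion 4 is not in it.
- The treatment-emergent window closes 3 days after the last infusion, nominally Day 10 + 3 = Day 13. AEs are collected to Day 28, so 28 − 13 = 15 nominal days fall outside it, and SAP 8.1 sends events that are not treatment-emergent to listings. If the only infusion was on Day 0, the window closes on Day 3.
- The AE/SAE model covers events at any time, but it sits among the secondary efficacy analyses, whose default set is the four-infusion set. SAP 5.7 and 8 put safety on the safety set. The text does not say which governs.

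**Why laboratory summaries do not give hepatotoxicity incidence.** The protocol's criterion is an AST/ALT rise above a stated level within 72 h of infusion. Table 2 places panels on Days 0, 3, 7 and 10. Nominally, the next panel after the Day 3 infusion comes 7 − 3 = 4 days (96 h) later, and none is scheduled after the Day 10 infusion. The ±3-day windows can shift this. A qualifying value may therefore come from an unscheduled test, and SAP 8.2 keeps unscheduled results out of tables.

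**Illustration of dilution (assumed counts).** The inputs are 60 and 40 patients (protocol, Investigational Plan) and the Beta(1,1) prior for proportions (SAP 7.1.4.1). With x active-arm patients affected and none on placebo, the posteriors are Beta(x+1, 61−x) and Beta(1, 41), so

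P(active rate higher) = 1 − ∏ k/(k+41), for k = 61−x to 61.

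- x = 6, one group: 1 − (55·56·57·58·59·60·61)/(96·97·98·99·100·101·102) = 0.976
- x = 3, the same six patients over two rows: 0.877 per row
- x = 2, over three rows: 1 − (59·60·61)/(100·101·102) = 0.790 per row
- x = 1, over six rows: 1 − (60·61)/(101·102) = 0.645 per row

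The result depends on the counts chosen. Grouped 8/60 v 1/40 gives 0.96, with a 95% interval for the risk difference of about −1 to 21 points. Both 8/60 v 2/40 and 6/60 v 1/40 give about 0.90.

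A simulation assumed five terms, each at 2%, 3% or 4% on active and 0.4% on placebo. The chance of a posterior above 0.95 was 0.43, 0.75 and 0.92 grouped, and 0.03, 0.14 and 0.33 for any one term. With 1% per term on placebo the figures were 0.18, 0.47 and 0.74 grouped, and 0.02, 0.11 and 0.28 for any one term. The 0.95 mark is also assumed, since the SAP sets no threshold for safety.

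**The case against.** Several objections have force.

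- **The gap starts in the protocol.** Its Study Endpoints lists and Safety Analysis paragraph omit the five categories, and SAP 2.1 follows those lists. This stands, and it is why the protocol lists must be reconciled. It does not cancel the two places that do name them.
- **Death is analysed.** A reader might infer that the SAP ignores death. It does not: fatal events are SAEs, AE outcome is tabulated, and death is an ordinal category. Only the dedicated count is missing.
- **Organ-class rows and laboratory tables already aggregate.** A reader might infer that every signal is scattered over preferred terms, or that liver and blood-count data are absent. Neither follows. Serious infections may sit largely in one organ-class row, and laboratory change is also a modelled secondary endpoint. Dilution affects events that cross rows.
- **The display list may hold the groupings.** The references to it in SAP 8.1 to 8.3 are broken, so this cannot be excluded. The supportable statement is that the SAP text specifies none, not that the endpoints will never be estimated.
- **EKG.** SAP 8.3 reads "The analyses of non-laboratory safety test results including physical examination and vital signs" and does not mention EKG. A reader might infer that a by-arm EKG comparison is needed. The documents do not support one: under Table 2, EKGs after baseline are done only if necessary, so the patients who have them are selected.
- **Thromboembolism and death are not among the five endpoints.** True. Their rows rest on the protocol's risk statement and the DSMB's remit, which is a weaker ground.
- **The numbers are constructed.** True. The SAP tables are descriptive, so per-row posteriors are not planned outputs. They show only how much evidence each row carries.

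**Conclusion.** The point holds as a gap in coverage. For all five named secondary safety endpoints, and for thromboembolic events, the SAP text gives no definition, no term grouping and no between-arm incidence analysis. Organ-class rows and laboratory summaries inform some of them, but without a count of affected patients by arm. Deaths are partly captured, with no all-cause count by arm to Day 28.

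The gap can be read from the text and rests on no figure. How much it would hide in this trial is unknown, because the documents give no event rates. The dilution figures assume counts, an even split over rows and one event per patient. They show the direction, not the size of a defect. The change should be made, because the trial would otherwise report no planned result for endpoints that its protocol names, or would choose the groupings late.

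**What to change.** 1. In SAP 2.1 and 8.1, add one table on the safety analysis set with seven rows: the five protocol endpoints, thromboembolic events, and all-cause death to Day 28. Each row gives patients with at least one event by arm, the risk difference with 95% credible interval, and the posterior probability.
2. Fix the term and laboratory criteria for each row before unblinding. For hepatotoxicity, use the AST/ALT criterion already in the protocol, and let unscheduled results count. If the allocation is already known, label the groupings post hoc.
3. State the time window of each row. The death row runs to Day 28 whatever the treatment-emergent window, and includes patients who received fewer than four infusions.
4. Reconcile the protocol's Study Endpoints lists and Safety Analysis paragraph with Criteria for Evaluation and Endpoints, so that the five categories are either endpoints throughout or not at all.
5. Do not add a by-arm EKG comparison.

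The cost is SAP wording, a blinded term list and one table. The SAP is still marked as a draft.

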## **8.2. Clinical Laboratory Analyses**

Laboratory evaluations including the analyses of Biochemistry laboratory tests (includes Comprehensive Metabolic Profile), Hematology laboratory tests (Complete Blood Count (CBC) and Coagulation Panel) and Urinalysis. The details of the planned displays are in **Error! Reference source not found..**

All laboratory parameters, including numerical urine analysis parameters will be summarised descriptively. Categorical urine analysis results will be summarized using count and percentage based on subjects.

Results of urine pregnancy test will be listed in individual subject data listings only.

Individual laboratory evaluations will be listed. In addition, a listing containing individual subject laboratory values outside the normal reference ranges will be provided.

Data recorded at unscheduled assessments will not be included in tables and figures but will be listed.

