9.3.5 Unscheduled Visits

The Investigator may at his/her discretion arrange for a patient to have an unscheduled assessment, especially in the case of adverse events (AEs) that require follow-up, or an AE considered by the Investigator to be possibly related to the use of the investigational product. The unscheduled visit page in the CRF must be completed.

10. Efficacy Assessments

7-Point Ordinal Scale

The ordinal scale is an assessment of the clinical status at the first assessment of a given study day. The scale is as follows:

- 1) Death
- 2) Hospitalized, on invasive mechanical ventilation or extracorporeal membrane oxygenation (ECMO)
- 3) Hospitalized, on non-invasive ventilation or high flow oxygen devices
- 4) Hospitalized, requiring supplemental oxygen
- 5) Hospitalized, not requiring supplemental oxygen
- 6) Not hospitalized, limitation on activities
- 7) Not hospitalized, no limitations on activities.

Complete Blood Count with Differential

The evaluation of the Complete Blood count with differential will help suspect the presence of a bacterial or viral infection with the predominance of either the neutrophils or lymphocytes. Generally, a healthy person’s blood count would not show out of range values in the differential in the absence of a pathological condition.

Comprehensive Metabolic Panel

The evaluation of glucose, calcium, proteins, electrolytes, liver enzymes and kidney function to determine status of metabolism. This panel is used to determine if treatments are having an effect on metabolic function.

CRP

C-reactive protein is considered to be an "acute phase protein," an early indicator of infectious or inflammatory conditions. CRP must be interpreted in the clinical context; no single value will be used to rule in or rule out a specific diagnosis.

CD4+/CD8+ ratio

The CD4+/CD8+ ratio is the ratio of T helper cells (with surface marker CD4) to cytotoxic T cells (with surface marker CD8). The CD4+/CD8+ ratio in the peripheral blood of healthy adults and mice is about 2:1, an inverted CD4+/CD8+ ratio (namely, less than 1/1) indicates an impaired immune system. A reduced CD4+/CD8+ ratio is associated with reduced resistance to infection, with ageing, and is an indicator of immunosenescence.

Natural Killer Cell Surface Antigen (CD3-CD56+ Marker Analysis)

Percentage CD3-CD56+ natural killers (NK⁺); absolute CD3-CD56+ natural killers (NK⁺); absolute lymphocyte count.

TNF-a

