The Investigator must review all laboratory reports and document the review. Any laboratory test result or change considered by the Investigator to be clinically significant should be considered an AE and recorded in the AE CRF. Clinically significant abnormal values occurring during the study will be followed until repeat test results return to normal, stabilize, or are no longer clinically significant.

Laboratory tests to be performed during the study:

Complete Blood Count with Differential	Natural Killer Cell Surface Antigen (CD3 ⁻ CD56 ⁺ Marker Analysis)
Complete Metabolic Profile	Il-10
Coagulation study (PTT/PT/INR)	CD4+ / CD8+ ratio
Urinalysis with pregnancy test	Creatine Kinase (CK)
C Reactive Protein	Troponin
Tumor Necrosis Factor alpha	Myoglobin (MB)
D-Dimer	VEGF
	Serum Ferritin

Adverse Events

An AE is any symptom, physical sign or disease that either emerges during the study or, if present at screening, worsens during the study, regardless of the suspected cause of the event. All medical and psychiatric conditions (except those related to the indication under study) present at screening will be documented in the medical history CRF. Changes in these conditions and new symptoms, physical signs, or diseases should be noted on the AE CRF during the rest of the study.

Clinically significant laboratory abnormalities should also be recorded as AEs. Surgical procedures that were planned before the patient enrolled in the study are not considered AEs if the conditions were known before study inclusion; the medical condition should be reported in the patient's medical history. Changes from baseline respiratory rate for non-ventilated subjects should also be considered as AE.

Serious Adverse Events (SAE)

A serious adverse event (SAE) is any AE that is:

- fatal
- life-threatening
- requires or prolongs hospital stay
- results in persistent or significant disability or incapacity
- Important Medical Events (IME): those events that may not result in death, be immediately life threatening, or require hospitalization. They may be considered a SAE when, based upon medical judgement, they may jeopardize the subject and may require intervention to prevent one of the other serious outcomes noted above. For example, drug overdose or abuse, a seizure that did not result in in-patient hospitalization, or intensive treatment of bronchospasm in an emergency department would typically be considered serious. (FDA, 21CFR312.32; ICH E2A and ICH E6)

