The reticuloendothelial system can sequester immature blood elements, theoretically resulting in hepatic injury. An acute elevation of the AST/ALT hepatic enzymes $> 900 \text{ U/dl}$ within 72h post-infusions will be considered an infusion related adverse event. This level is based upon the organ system scoring definitions for moderate hepatic failure and corresponds to the CTCAE v4.03 Grade 3 adverse event. It is unlikely that "end vessel" micro-thrombosis would occur in the liver due to the dual blood supply of the liver and the lung is the first pass organ. A CMP will be obtained at follow-up visits.

Coagulation Cascade:

A coagulation panel will be obtained at screening, baseline, infusion and the follow-up visits. The patient will be monitored for the development of venous thromboembolic events (see pulmonary monitoring above) as well as for the development of clinical deep vein thrombosis (limb swelling, tenderness, discoloration).

The types of risk associated with HB-adMSCs are also stated in the Informed Consent Form (See ICF)

Minimization of Risks

Although the risk to subjects participating in the study is anticipated to be minimal, the clinician, at his/her discretion, will not collect data from those individuals for whom collection is judged to pose an unusually high risk of physical or mental harm or discomfort.

Participation in this study poses moderate risk to study personnel related to potential pathogens that may be present in the subject's specimens which are then expanded during the culture process. These risks will be minimized by adherence to the principles of universal precautions and by conducting the planned testing on blood from the subject at screening for particular pathogens of concern.

Personnel should wear appropriate personal protective equipment to avoid contact of the eyes or skin with hazardous materials or products derived from biological sources.

Subjects will be advised to follow current federal guidelines regarding COVID-19 such as the following:

- Clean and wash hands often with soap and water for at least 20 seconds upon arrival and exit of the site.
- Use hand sanitizer that contains at least 60% alcohol
- Avoid touching your eyes, nose, and mouth with unwashed hands
- Avoid close contact
- Adhere to social distancing guidelines and maintain at least 6' of distance with others

General procedures for study personnel include:

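### SAP 8.2 keeps every unscheduled laboratory value out of tables and figures and names no worst-value table, so as scheduled no laboratory value after the fourth infusion can be compared between arms

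*SAP*

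**What the plan says.** SAP 8.2 (Clinical Laboratory Analyses) covers biochemistry, haematology, coagulation and urinalysis. Its summary rule is "All laboratory parameters, including numerical urine analysis parameters will be summarised descriptively", and its rule for off-schedule data is "Data recorded at unscheduled assessments will not be included in tables and figures but will be listed". It adds that "a listing containing individual subject laboratory values outside the normal reference ranges will be provided". Its pointer to the planned displays is a broken cross-reference.

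SAP 7.2.4.2 also models clinical laboratories by arm, using Visits 2 to 5 only.

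In the protocol, Unscheduled Visits (9.3.5) lets the investigator arrange an "unscheduled assessment, especially in the case of adverse events (AEs) that require follow-up". Clinical Laboratory Parameters makes any result judged clinically significant an adverse event (AE) and requires repeat testing: "Clinically significant abnormal values occurring during the study will be followed until repeat test results return to normal". Hepatic Risks sets a criterion of AST/ALT above 900 U/dl, which "within 72h post-infusions will be considered an infusion related adverse event". The safety endpoints include hepatotoxicity and cytopenias, and "Clinically significant changes in laboratory values, vital signs, weight, and physical examination results will also be measured".

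SAP 8.1 counts an AE as treatment-emergent up to 3 days after the last infusion. Other AEs are listed, apart from the separate tables for serious AEs and AEs leading to withdrawal.

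**The concern.** Unscheduled samples are taken mainly because something has happened to the patient, so they are likely to contain more abnormal results than routine draws. Excluding them from by-visit means is sound, because such means need a common schedule. The difficulty is that the SAP names no other by-arm laboratory display that would use them.

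Laboratory change is part of this trial's safety question: the protocol's safety hypotheses refer to harmful laboratory changes related to the drug. If transient hepatic, blood-count or coagulation abnormalities were more frequent in one arm and fell between or after the scheduled draws, the laboratory tables could not show it. A reader would have to reconstruct the comparison from patient-level listings.

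**Working it through.** The plan states no figure to reproduce. The check sets the draw schedule against the infusion schedule.

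**Inputs.** Infusions are on Days 0, 3, 7 and 10. Panels are at screening and on Days 0, 3, 7 and 10, each visit ±3 days (Protocol Table 2). Day 28 is a phone call with the ordinal scale and no panel in Table 2. I take the order of the infusion-visit lists (blood collection, then infusion) as the order in time. Planned arms are 60 and 40.

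**72-hour windows on nominal days**

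| Infusion | Window | Scheduled panel after that infusion, within the window |
|---|---|---|
| 1 | Day 0 to 3 | Day 3, at the 72-hour limit |
| 2 | Day 3 to 6 | none (next is Day 7, at 96 hours) |
| 3 | Day 7 to 10 | Day 10, at the 72-hour limit |
| 4 | Day 10 to 13 | none (no later panel in Table 2) |

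So 2 of 4 windows have no nominal panel. The ±3-day allowance weakens this for infusion 2: a Day 7 visit held on Days 4 to 6 falls within 72 hours of a Day 3 infusion. It also works the other way, since a late visit moves the panel after infusion 1 or 3 outside 72 hours. Only the gap after infusion 4 is independent of visit timing, because no panel follows that visit.

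**Share of follow-up.** After Day 10: 28 − 10 = 18 days, and 18/28 = 64%, with no scheduled panel. After the treatment-emergent cut-off, nominally Day 10 + 3 = Day 13: 28 − 13 = 15 days, and 15/28 = 54%. In that period a non-serious laboratory AE that does not lead to withdrawal is only listed.

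**What still reaches a by-arm table**

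| Abnormality | Route |
|---|---|
| Any value at a scheduled panel | Laboratory summaries |
| Judged clinically significant, onset by about Day 13 | Treatment-emergent AE tables |
| AST/ALT above 900 U/dl within 72 hours | An AE by definition; on day counts inside the treatment-emergent window |
| Serious, or leading to withdrawal, any time | Own tables in SAP 8.1 |
| Unscheduled, not judged significant, not meeting the AST/ALT criterion | Listing only |
| Non-serious laboratory AE, not leading to withdrawal, onset after about Day 13 | Listing only in SAP 8.1 |

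The last two rows are the gap.

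**Illustration.** The documents give no incidence, so assume that a share p of patients has one abnormality of the fifth kind within 72 hours of an infusion, equally likely after each of the four, and that an unscheduled sample finds every one falling where no panel is drawn. If a share f of windows has no panel, the expected number missing from an arm of n is n × p × f, and the chance of at least one is 1 − (1 − p × f)^n.

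| f | p | HB-adMSCs (n = 60): expected; chance of ≥1 | Placebo (n = 40): expected; chance of ≥1 |
|---|---|---|---|
| 1/4 (infusion 4 only) | 3% | 0.45; 36% | 0.3; 26% |
| 1/4 | 10% | 1.5; 78% | 1.0; 64% |
| 2/4 (nominal days) | 3% | 0.9; 60% | 0.6; 45% |
| 2/4 | 10% | 3.0; 95% | 2.0; 87% |

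These are upper bounds, since an abnormality that nobody samples is lost under any rule.

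**The case against.** The strongest reply is that the AE system already carries what matters. A clinically significant laboratory result is an AE whichever sample shows it, and the AST/ALT criterion needs no judgement of significance. Hepatotoxicity and cytopenias are defined as incidences of specific AEs, so they are read from AE data and not from laboratory means. Many unscheduled repeats will follow events already recorded and will show recovery, not peaks. SAP 7.2.4.2 also models whether a patient had any AE at any time in the study, so late events are not wholly absent from comparison. Unscheduled and out-of-range values are listed. Finally, the broken cross-reference means a display list might include a shift table.

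Most of this stands, and it rules out three stronger inferences that a reader might draw:

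- That abnormal values come only from unscheduled assessments. Scheduled panels find them too, and those are tabulated.
- That half of the post-infusion windows can be filled only by excluded data. That is true on nominal days, but the visit windows leave only the gap after infusion 4 certain.
- That the protocol's hepatic event would vanish from the comparison. It is an AE within the treatment-emergent window.

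The reply does not close the gap. The any-AE model is not specific to laboratory events, and by SAP 7.2.3 its default population is patients who received all four infusions. Listings do not compare arms. A display list that cannot be seen cannot be relied on, and the text of SAP 8.2 excludes unscheduled data from every table and figure.

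**Conclusion.** The point holds in limited form. SAP 8.2 withholds collected safety data from comparison between arms for two groups: unscheduled abnormalities neither judged clinically significant nor meeting the AST/ALT criterion, and non-serious laboratory AEs, not leading to withdrawal, that start more than 3 days after the last infusion. The certain part is the period after infusion 4, which is 18 of 28 days (64%) with no panel in Table 2. The window after infusion 2 is a nominal gap only.

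This rests on blood being drawn before the infusion at each visit, on Table 2 governing the draws, on reading the treatment-emergent label in SAP 8.1 as one category despite its varying abbreviations, and on no worst-value table existing in a display list that the SAP does not show.

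A reader might go further and conclude that the trial would wrongly report laboratory safety as balanced. The documents do not support that, because serious and clinically significant events have other routes into by-arm tables. This is an inexpensive improvement to safety reporting.

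**What to change.** Keep the by-visit laboratory summaries on scheduled data. Replace the blanket exclusion in SAP 8.2 with text such as:

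*Unscheduled values are excluded from by-visit summaries. For each hepatic, blood-count and coagulation parameter, the worst post-baseline value from all scheduled, unscheduled and early-discontinuation samples to Day 28 will be tabulated by arm as a shift from baseline (low, normal, high) in the Safety analysis set. The number of patients meeting the protocol's AST/ALT criterion as written, and the number of samples per patient, will be tabulated by arm.*

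The cost is a short SAP edit and two or three tables from data already collected and listed; the SAP is still marked draft. The drawback is that worst values rise with sampling frequency, and sicker patients are sampled more often. The sample counts make that visible, and blinding limits differences in sampling between arms.

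Repair the cross-reference so that the planned displays can be checked. Separately, reconcile the protocol's Hepatic Risks and Coagulation Cascade text, which places a metabolic and a coagulation panel at follow-up visits, with Table 2 and the Day 28 section, which schedule neither. A Day 28 sample would in any case fall about 18 days after infusion 4 (28 − 10), outside the 72-hour window.
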